Appendix A Study timeline

Appendix B Supplemental tables - Statistical calculations for secondary endpoints

Background

HIV and non-communicable diseases (NCDs) are increasing in Africa. Effective antiretroviral therapy (ART) has promoted immunologic recovery, but at the cost of adverse metabolic complications and negative health outcomes, most commonly referred to as non-communicable diseases (NCDs), that have emerged as a major health concern among long-term ART-treated adults.¹⁻⁵ We are faced with a new challenge: namely, addressing morbidity and mortality from NCDs—specifically kidney disease plus heart disease, stroke, diabetes, and metabolic complications, and non-AIDS associated cancers-that increase with age and may be related to HIV, its treatment, host genetic factors, and/or modifiable risk factors.⁶⁻¹¹ Deaths due to NCDs are rapidly trending to occupy a larger share of deaths and disability-adjusted life years (DALYs) in resource-constrained settings. More than 38 million persons die each year from NCDs, with the vast majority (82%) residing in low- and middle-income countries (LMICs).¹² Current projections show that by 2020, 73% of all deaths worldwide will be due to NCDs and that the burden of NCDs will rise by more than 60% in LMICs, with the largest increases in NCD deaths in Africa. HIV infection and ART interact with NCD risk factors in complex ways, and research into this important area has so far been largely based on data from high income countries.¹³ Figure 1 (below) displays the share of agestandardized disability-adjusted life years (DALYs) among reproductive-aged adults for NCDs (blue), communicable diseases (red), and external causes (green) for Western sub-Saharan Africa (SSA) and North America, from the Global Burden of Disease project.¹³ Darker color shades represent diseases that are increasing more rapidly.

Figure 1: Distribution of DALYs by region of the world (North America vs. Western SSA), ages 15-49 years, 2016.

North America

Western SSA

The burden of HIV-associated kidney disease in Africa is substantial. Although ART has substantially reduced the impact of HIV-associated kidney disease in the U.S., the HIV epidemic continues globally in kidney disease-susceptible African-descent populations.^{14,15} Chronic kidney disease (CKD), defined as the presence of proteinuria (defined as urine albumin/creatinine ratio >300 mg/g) and/or reduced eGFR (defined as. <60 mL/min/1.73m²), is at least 3–4 times more frequent in Africa than in developed countries.¹⁶⁻¹⁸ The reported prevalence of CKD in HIV positive ART-naive patients varies across SSA, ranging from 6 to 48%, with the highest prevalence reported in Nigeria, the most populous nation in Africa.¹⁷⁻²² Stanifer et al ²³, in their recent meta-analysis of 90 studies in SSA, found that the overall prevalence of CKD from 21 medium- and highquality studies was 13.9% [95% CI: 12.2-15.7], and that among people with HIV, the prevalence of CKD was highest in Nigeria, Zimbabwe, and Uganda. In studies conducted by Mulenga et al.¹⁹, the prevalence of kidney dysfunction (defined as eGFR of < 90 mL/min/1.73m²), was 33.5% among HIV positive ART-naïve adults presenting for care at a large urban clinic in Lusaka, Zambia. Mulenga et al.¹⁹ also showed that ARTnaïve patients with kidney dysfunction in Zambia had a 4-fold higher mortality rate compared to those with normal renal function. CKD affects an estimated 14% of adults in SSA, but very little research has been done on the cause, progression, and prevention of CKD in this region.²¹ As part of the Human Heredity and Health in Africa (H3Africa) Initiative, the H3Africa Kidney Disease Research Network ²⁴ was established to study prevalent forms of kidney disease in SSA and increase the capacity for genetics and

genomics research. Dr(s) [name] and [name] are involved with the H3Africa initiative. Our proposed work does not overlap with any ongoing/planned work in this consortium, and we will share all study findings with them.

Host genetics play an important role in CKD risk. Because certain HIV-related kidney diseases (HIV-associated nephropathy [HIVAN] and focal segmental glomerulosclerosis [FSGS]) emerge exclusively (HIVAN) or largely (FSGS) in persons of African descent (~20-fold greater risk than non-African descent counterparts), several studies have sought associations between genetics and a predisposition to CKD in these patients.²⁵⁻³⁷ Genovese et al.³⁷ described two risk alleles in the APOL1 gene, a 2-allele haplotype (G1) that consists of the 2 derived non-synonymous coding variants rs73885319 (S342G) and rs60910145 (I384M), and a G2 allele that consists of a 6-base pair deletion (rs71785313) that removes 2 amino acids (NYK388K).³⁷ [name], [name], Pollak et al.^{30,36-} ³⁸ have shown that the APOL1 high-risk genotype (defined by the carriage of two APOL1) risk alleles) confers sizeable odds ratios (OR) for FSGS (OR = 17), HIVAN (OR = 29 in the US; 89 in South Africa), and hypertension-attributed end stage kidney disease (ESKD) (OR = 7). These variants are present only on African-origin chromosomes. The frequency of the risk alleles is highest in West Africa, specifically in Nigeria among persons of Yoruba (>50%) and Igbo (>50%) descent.^{39,40} As the APOL1 effect is largely recessive (2 risk variants), ~25% of the population is at substantially increased risk of kidney disease. In the setting of untreated HIV infection, we have estimated that ~50% of individuals carrying high-risk genotypes will develop CKD.^{41,42} Even when HIV replication is suppressed, APOL1 high-risk individuals remain at greatly increased risk for FSGS and hypertension-attributed ESKD, similar to HIV-negative APOL1 risk individuals.25

Microalbuminuria is an important early marker of kidney disease, including in HIV positive adults. There is a continuum of kidney disease, typically defined by increasing stages of CKD. In some forms of kidney disease, such as diabetic nephropathy, the earliest detectable abnormality is microalbuminuria, which may progress to macroalbuminuria and finally to nephrotic range proteinuria. Albuminuria is an independent risk factor for cardiovascular and renal disease and a predictor of end organ damage.⁴³ Microalbuminuria (urine albumin/creatinine ratio (uACR) = 30-300 mg/g) can signify either glomerulosclerosis or glomerular microvascular dysfunction (often associated with systemic microvascular dysfunction) has been used in the early detection of several disease states, i.e. preeclampsia, diabetic nephropathy, and medication-induced nephrotoxicity.⁴³ As a result, various guidelines have recommended assessment of urinary protein in adults with hypertension or diabetes, and even in the general population to identify at-risk persons. Proteinuria has also been associated with decreased CD4+ cell counts and higher plasma viral loads among HIV-positive individuals, as well as increased systemic T-cell activation and more rapid progression to AIDS.⁴⁴⁻⁴⁶ Microalbuminuria and macroalbuminuria are also important risk factors for mortality in ART-treated HIV-positive individuals, probably due to their role as a marker for inflammation and endothelial activation.⁴⁷⁻⁴⁹ Even very low levels of albuminuria (uACR = 10-30 mg/g) have been associated with adverse cardiovascular and renal events.^{44,50} Gerstein et al., ⁴⁴ evaluating older patients with at least one risk factor for cardiovascular disease, found that routine screening for albuminuria identifies people at high risk for cardiovascular events.⁴⁴ Current guidelines recommend that all HIV positive adults with significant proteinuria of grade \geq 1+ (by dipstick analysis) and/or reduced kidney function (eGFR < 60 ml/min per 1.73m²) be referred to a nephrologist for additional quantification of urinary protein excretion and/or a kidney biopsy. While

therapy for HIV-associated kidney disease needs to be individualized, waiting for overt proteinuria may miss a potential earlier window for intervention to more effectively forestall progression to the more advanced stages of CKD. Microalbuminuria is an established screening test to detect early diabetic nephropathy, and there is growing interest to screen for microalbuminuria to identify early HIV-associated kidney disease in patients. Hadigan et al.⁵¹ found the period prevalence of microalbuminuria in their U.S.based HIV cohort to be 14%, and patients with microalbuminuria were more likely to have hypertension, metabolic syndrome, and immunosuppression (CD4+ cell count < 200 cells/mm).^{32,51} Lastly, they determined that a single normal uACR determination effectively excluded microalbuminuria, whereas an elevated uACR required confirmation.⁵¹ The UK National Institute of Health and Clinical Excellence (NICE) guidelines for CKD suggest defining pathologic albuminuria by a random urine albumin/creatinine ratio (uACR) > 30 mg/mmol (~300 mg/d).⁵² Gansevoort et al.⁵³ demonstrated that progressively higher levels of ACR were predictive of worse renal outcomes across a range of eGFR values. In particular, detection of an increase in protein excretion had diagnostic and prognostic value in the initial identification and confirmation of kidney disease, and the quantification of protein excretion could be of considerable value in assessing disease progression, as well as treatment efficacy.^{43,45,49,54} 24-hour urine collection has been considered the "gold standard" for urinary protein collection, but this technique is cumbersome.⁵⁴ Furthermore, Heerspink et al.⁵⁵ recently showed that in diabetic patients, first morning void uACR was superior to 24-hour urine protein or albumin in predicting renal outcomes. This suggests that 24hour urine protein collections are no longer the gold standard. Easier alternatives include first morning voided or spot (random) samples, with data supporting the use of random uACR to accurately characterize protein and albumin excretion in adults with renal disease.⁵⁶⁻⁶⁵ However, uACR measurements are not standard practice when screening HIV-positive patients for underlying kidney abnormalities, although their routine use is gaining popularity.

HIV-associated kidney disease is common in Africa. HIV-positive adults are at risk for several chronic kidney diseases, including glomerular disease (collapsing glomerulopathy; commonly referred to as HIVAN, immune complex glomerulonephritis, FSGS, thrombotic microangiopathy, etc.), and tubulointerstitial disease associated with infections and specific medications (i.e. tenofovir). ^{34,66-73} The most severe of these, HIVAN, is a direct result of HIV replication in the kidney and occurs almost exclusively in persons of African descent.⁷¹⁻⁷³ Other hallmarks include proteinuria and normal/increased kidney size with increased echogenicity.74-76 Renal disease, especially glomerular disease, is more prevalent in Africa and seems to be of a more severe form than that found in Western countries.⁷⁶ The true prevalence of HIVAN worldwide is not known- earlier studies suggested that approximately 10% of HIV positive, untreated persons with recent African ancestry develop HIVAN at some point in their HIV disease course;⁷⁷⁻⁸⁰ however, a paucity of African data exists describing the prevalence of HIVAN.⁸⁰ We will not be performing renal biopsies in this study and therefore will examine HIV-associated kidney disease (not HIVAN specifically). Of relevance to our proposed study as we aim to intervene aggressively and early in the course of our Nigerian patients' kidney disease continuum, Han et al.⁸⁰ found 6 of 7 (86%) patients in their cohort with persistent microalbuminuria, when biopsied, to have structural kidney disease (HIVAN). Given the lack of dialysis and renal transplant options for the majority of Nigerians with HIV infection, our pharmacological research approach to halt or slow progression of CKD is especially urgent for SSA and may also be relevant for higher resource settings.

Renin angiotensin aldosterone system (RAAS) inhibition can be used to reduce kidney complications. The renin-angiotensin aldosterone system (RAAS) is recognized as a central driver of the pathophysiology of CKD, based on numerous clinical trials in individuals with diabetes.^{81,82} Renal dysfunction can be regarded as a continuum that extends from endothelial dysfunction to microalbuminuria, macroalbuminuria, ESKD, and ultimately death. All stages of this continuum are associated with progressively increasing cardiovascular risk.⁸³ Preventing the development and progression of kidney disease does require tight blood pressure control, but due to the important role of the RAAS in the pathogenesis of diabetic kidney disease, agents that inhibit this system (angiotensin converting enzyme inhibitors (ACEis) or angiotensin receptor blockers (ARB's) are recognized first line therapy,⁸³ offering both effective blood pressure lowering and direct actions on the kidney. Numerous studies have documented the efficacy of RAAS inhibition as a means to slow the progression to CKD among at-risk diabetics.^{81,82,84-90} Maione et al.,⁹¹ in their systematic review of ACEi's and ARBs in patients with microalbuminuria, found a significant reduction in the risk of all kidney outcomes with ACEi's compared to placebo or no treatment (ESKD: 9 RCTs, 7988 patients, RR 0.67 [0.54–0.84]; doubling of serum creatinine: 9 RCTs, 8460 patients, RR 0.62 [0.46–0.84] and progression from micro- to macroalbuminuria: 18 RCTs, 2888 patients, RR 0.49, [0.36–0.65]. There was also a significant increase in the likelihood of regression from micro- to normoalbuminuria (15 RCTs, 1860 patients, RR 2.99 [1.82-4.91] (see Section D.2 Sample size justifications). The end-organ protective effects of ACE is appear strongly related to their reactive oxygen species (ROS) lowering effects, and it has been hypothesized that high levels of ROS contribute to the pathogenesis of NCDs, including end-organ kidney complications.85,92-97

1.0 Rationale and Specific Aims

Nigeria is home to the fourth largest HIV-positive population in the world, having an estimated ~ 1,900,000 people living with HIV and 53,000 AIDS-related deaths annually.⁹⁸ Non-communicable diseases (NCDs), including kidney disease, among HIV-positive and HIV-negative adults in sub-Saharan Africa (SSA) represent a burgeoning epidemic. This study will be the first of its kind providing randomized controlled trial (RCT) evidence informing the optimal strategy to manage HIV-positive adults with albuminuria, particularly those with *APOL1* risk alleles who are genetically susceptible to kidney disease and potentially other life-threatening (i.e. cardiovascular) end-organ complications. Confirmation of the highest rates of adult HIV-positive populations globally carrying *APOL1* high-risk genotypes (~ 25%) would have significant implications for clinical care (including monitoring strategy) of persons in Nigeria and the West African region as a whole.

This study of HIV kidney disease is innovative for the following reasons:

1) Microalbuminuria among HIV-positive adults in Nigeria most likely represents underlying early structural kidney disease. This was the case in a small kidney biopsy series performed among HIV-positive adults presenting with persistent microalbuminuria in South Africa, of whom 6 of 7 were found to have HIV-associated nephropathy.⁸⁰ The present study will be the first to evaluate therapy to treat microalbuminuria in this population with the goal of preventing the progression of kidney disease.

2) *APOL1* variants are a major driver of kidney disease in HIV-positive persons. Most existing data on APOL1 risk variant prevalence are based on DNA from studies with very small sample sizes among specific African ethnic groups. This will be the largest genetic risk variant survey to date among individuals in West Africa, the region of the world with the highest documented carriage rates of the *APOL1* high-risk (HR) genotype.

3) If early therapy can reduce albuminuria, it could also reduce the burden of HIVassociated CKD and associated morbidity and premature mortality. Such findings would make a strong case for the adoption of population-based screening for albuminuria using uACR measurements (compared to less accurate urine dipstick and cumbersome 24hour urine protein measurements). This testing would also greatly assist in the identification of persons in need of early intervention. In resource-poor settings, where access to therapies for ESKD (dialysis and kidney transplantation) are not widely available, prevention of CKD may prolong life.

4) Determining if the presence of an *APOL1* risk genotype correlates with ESKD risk (microalbuminuria, reduced eGFR, and/or early CKD), as well as determining whether it influences longitudinal renal outcomes among patients with prevalent albuminuria, is novel and will inform treatment guidelines and result in significant public health benefits, particularly if our results show that affordable and readily available treatment can be instituted early in the disease continuum; AND

5) Various interventional studies involving small numbers of subjects have been performed showing that the provision of RAAS inhibition is safe and may be beneficial when given to HIV-positive adults with HIV-associated nephropathy manifesting with varying levels of proteinuria.⁹⁹⁻¹⁰⁶ Despite strong rationale and encouraging preliminary data, the role of RAAS inhibition in HIV-positive subjects with or at-risk for HIV-associated kidney disease remains to be confirmed by well-designed and adequately powered randomized controlled trials. The R3 study as designed is well poised to be the first RCT to provide definitive evidence regarding the role RAAS inhibition as adjunctive therapy to standard ART could play in the large numbers of HIV-positive adults at risk for long-term kidney complications. Such guidance is especially relevant in West Africa where the prevalence of the *APOL1* high risk genotype is highest globally. In addition, the promising pharmaceutical approach of the R3 study is particularly important in sub-Saharan Africa, where treatment options for ESKD (i.e. dialysis and transplantation) are extremely limited.

To accomplish our goals, we will pursue the following Specific Aims:

1.1 Specific Aim 1

Specific Aim 1: To determine the prevalence of *APOL1* renal risk variants among 2,600 HIV-positive individuals in Nigeria and assess whether *APOL1* HR status correlates with prevalent albuminuria, eGFR, and/or prevalent CKD (defined as macroalbuminuria or eGFR <60 ml/min/1.73 m²) in this population.

Hypothesis: ~25% of those screened will carry the *APOL1* HR genotype, which will be associated with albuminuria, lower baseline eGFR, higher uACR, and higher rates of prevalent CKD.

Definitions: Microalbuminuria will be defined as having a mean uACR of 30-300 mg/g. CKD will be defined by the presence of proteinuria or an eGFR of < 60 ml/min/1.73m².

Study Population: We will determine the prevalence of *APOL1* risk variants in a large group of HIV-positive adults (n = 2,600) in Nigeria and correlate them with early markers of kidney disease; namely microalbuminuria, reduced eGFR, and CKD. All consecutively seen HIV-positive ART-experienced (6+ months) adults (\geq 18-70 years of age) presenting for care at AKTH will be approached for enrolment into this study. **NOTE**: We will be enrolling ART-experienced adults (on ART for 6+ months). Specifically, if on ART for 6-12 months, then subjects need to have a plasma viral load value < 20 copies/mL from their 6-month blood draw, and if on ART for > 12 months, then enrolled participants need to have a suppressed viral load result (i.e. < 20 copies/mL) on their most recent viral load blood draw---which needs to be within the past 6 months). Routine viral load monitoring has only recently been implemented at our study site in north-central Nigeria, and by enrolling only patients with recent evidence of viral suppression, we will do our best to eliminate ongoing HIV-associated viral replication in non-adherent persons as a potential contributing cause to immune activation and therefore NCD end-organ complications, including kidney disease.

1.2 Specific Aim 2

Specific Aim 2: To assess whether RAAS inhibition with an ACEi compared to placebo, significantly reduces incidence of albuminuria or reduced eGFR among 280 HIV-positive individuals with microalbuminuria who are receiving ART.

Hypothesis: After two years,

- A significantly higher proportion of participants in the intervention vs. SOC arm will regress from microalbuminuria to normoalbuminuria (uACR<30 mg/g); anticipated hazard ratio = 2.5.
- Significantly higher proportions of participants in the SOC arm (60% vs. 25% in the intervention arm) will progress from microalbuminuria to macroalbuminuria (uACR>300 mg/g).
- Albuminuria will fall by an average of 40% in the intervention arm and increase by an average of 10% in the SOC arm.

Study population: All HIV-positive ART-experienced (6+ months) screened individuals (n = 2,600) found to have i) confirmed microalbuminuria (mean uACR between 30-300 mg/d obtained at 2 separate measurements at least 4 and no more than 8 weeks apart), (NOTE: based on variability of individual uACR measurements, we also plan to call back Aim 1 participants having normoalbuminuria (especially those with an average uACR value in the 20-29 mg/g range) as well as Aim 1 participants having macroalbuminuria), and ii) fairly well-preserved renal function, namely an eGFR > 60 ml/min/1.73m²; will be approached for enrollment into this study. Based on recent studies at AKTH among HIV positive adults, we anticipate that a minimum of 18% of screened patients (n~460) will be eligible. Therefore, with a target sample size equal to

280 (see Section 10.0), 59% of eligible patients would need to consent for this Aim 2 study.

Primary Endpoints:

- i) Regression from microalbuminuria (uACR=30-300 mg/g) to normoalbuminuria (uACR < 30 mg/g)
- ii) Progression from microalbuminuria (uACR=30-300 mg/g) to macroalbuminuria (uACR > 300 mg/g) by study arm
- iii) Mean change in uACR

Secondary Endpoints:

i) Doubling of serum creatinine from baseline; ii) All-cause mortality (**NOTE**: Planned follow-up is two years for all participants), iii) Proportion experiencing a 40% decline in eGFR (using CKD-EPI-Cr-CyC equation), iv) Mean change in eGFR over time (using CKD-EPI-Cr-CyC equation), and v) change in clinical/performance status (as ascertained via two measures, specifically the WHO quality of life (WHOQOL-HIV) tool (31 questions)^{107,108} and the Karnofsky performance score)¹⁰⁹.

1.3 Specific Aim 3

Specific Aim 3: To determine whether the *APOL1* HR genotype is associated with worse longitudinal kidney outcomes among HIV-positive Nigerians with prevalent albuminuria, with regard to progression of albuminuria and eGFR decline.

Hypothesis: After two years of follow-up, independent of baseline uACR, eGFR, and/or treatment assignment:

- Study participants with the HR genotype will have a more rapid kidney function decline (median eGFR change) compared to those with the LR genotype.
- Study participants with the LR genotype will have 30% lower mean uACR values (compared to baseline) compared to study participants with the HR genotype.

Study population: All enrolled Aim 2 study participants who completed the study, namely, two years of study follow-up. However, to improve our power to evaluate the influence of *APOL1* risk allele status on key renal outcomes, we will include all enrolled Aim 2 study participants that completed a minimum of one year of clinical follow-up, meaning that if they were lost to follow-up after completing their one-year study visit, we will include them in our Aim 3 genetics outcome analyses.

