Longitudinal Study Assessments: All enrolled patients will undergo the following tests at baseline and then every 3 months while on study, until completing 2 years of followup: serum cystatin C, blood pressure, serum electrolytes (creatinine, potassium, sodium, chloride, bicarbonate, and urea), and uACR. Clinical performance status (as measured via the WHOQOL-HIV tool and the Karnofsky performance score) will be evaluated at baseline and at 12 and 24 months. If participant is a female with reproductive potential, she will undergo urine pregnancy testing every 3 months (please see below in **NOTE**). All enrolled aim 2 study participants will have their APOL1 genotype data (i.e. whether HR or LR genotype) available prior to completing study follow-up (see Study Timeline). All patients will undergo routine standard laboratory monitoring as per existing guidelines; specifically, CD4+ cell count and viral load testing (q 6 monthly), liver function test monitoring (at month 1, 3, and 6, and then q 6 monthly following ART initiation), etc., as per Nigeria standard of care (SOC). All enrolled patients will undergo a blood pressure check and have serum electrolytes tested at week 1 and month 1 following study initiation and any changes in dose as part of a brief safety check. All enrolled patients will undergo hepatitis B and C screening at baseline. Additional funds have been allocated for patients to undergo unscheduled safety monitoring (up to two additional times per year) as needed, while on study.

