enroll 280 eligible patients from Specific Aim 1 for 1:1 randomization in our RCT for Specific Aim 2. Based on our prior experience with ongoing RCTs in the study location, we anticipate that enrollment into Aim 2 will take 12 months and there will be 10% loss to follow up at end of year 2, yielding 252 patients on study (126 per arm). Aim 2A: At 2 years, we hypothesize that a higher proportion of intervention participants will regress from microalbuminuria to normoalbuminuria (uACR < 30 mg/g) with a hazard ratio (HR)= 2.50. Using the logrank test, we will have approximately 80% power if the rate of regression in the SOC arm is at least 12%, and 90% power if that rate is 16% or higher with a 1.7% type I error¹³⁶. (The type I error rate was set at 5%/3=1.7% to account for multiple testing and the fact that we have 3 primary endpoints.) See Tables 3 and 4. Aim 2B: At 2 years, we hypothesize that a higher proportion of patients in the SOC arm. namely 60% vs. 25% in the intervention arm (HR≈0.42), will progress from microalbuminuria to macroalbuminuria (uACR > 300 mg/g). With 126 patients per arm (after removing 10% loss to follow-up), we will have >95% power for Aim 2B with a 1.7% type I error. See Tables 5 and 6. Figure 3 shows changes in Aim 2A power for varying SOC regression rates and changes in Aim 2B power for varying sample size. The sample size for Aim 2C is such that we will have approximately 80% power to detect at the alpha=0.017 level a difference in the log-transformed mean uACR of 0.24, which is approximately 0.41 standard deviations. These power calculations are likely conservative, as they do not incorporate baseline covariates, which will be included in the actual analyses (see below) and should improve power; in addition, the uACR analysis will incorporate multiple longitudinal measures per person whereas these power calculations only assume a single final measurement per person.

The sample size was chosen to have sufficient power for all primary endpoints. Tables S1-S8, investigating power and detectable alternatives for the secondary endpoints with a total sample size of 280 are provided in Appendix B. In short, we anticipate low power to detect differences between intervention arms in the doubling of serum creatinine, all-

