Statistical analysis plan: Our first approach will be to perform an intent-to-treat analysis, but we will also perform an on-treatment analysis to compare these data and present all available findings. *Primary analysis*: We will test the hypotheses that regression and progression rates are different across arms using multivariable Cox regression models with the intervention variable (randomization to RAAS [yes/no]) as the primary predictor variable, adjusting for baseline (pre-randomization) covariates including baseline uACR, *APOL1* renal risk variants, CD4+ cell count, blood pressure

ART regimen (DTG vs. other), and the presence/absence of comorbid medical conditions (hypertension, cardiovascular disease). To relax linearity assumptions, baseline uACR will be included in models using restricted cubic splines.¹³⁸ Primary analyses will be intention to treat, although we also plan to perform "per protocol" analysis. We will also test the impact of study arm on uACR using a linear mixed effects model to account for within patient correlation with the outcome of 3-monthly uACR values (with primary endpoints obtained by evaluating the uACR and other key renal outcomes at 18 and 30 months given that all enrolled study participants will not be placed or sustained on their maximum tolerated lisinopril dose or matched placebo until 6 months after study enrollment). The model will also adjust for the baseline covariates given above. For this analysis, we anticipate log-transforming uACR to meet modelling assumptions, although other transformations will be considered if needed.

Secondary analyses: Analyses for secondary endpoints will be similar to that described above. Time-to-event outcomes (doubling of serum creatinine from baseline, all-cause mortality, 40% decline in eGFR, and tenofovir toxicity) will be assessed using multivariable Cox regression models. Continuous outcomes (eGFR, quality of life metrics, and blood pressure) will be analyzed using mixed effects models after proper transformation of the outcome variable, if necessary. Baseline covariates listed above will be included in all secondary analyses.

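### The month-30 reading of the primary endpoints lies beyond the two-year follow-up, and the regression and progression events are defined by thresholds alone

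*Combined protocol and SAP*

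**What the plan says.** **Endpoints.** Section 1.2 gives the first primary endpoint as "Regression from microalbuminuria (uACR=30-300 mg/g) to normoalbuminuria (uACR < 30 mg/g". The second is the corresponding move above 300 mg/g, and the third is mean change in uACR. For the first two, nothing is said about the number of samples, confirmation, persistence, or how someone who crosses back is counted.

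**Hypothesis and power.** Section 1.2 expects, after two years, that "A significantly higher proportion of participants in the intervention vs. SOC arm will regress from microalbuminuria to normoalbuminuria", and in the same sentence anticipates a hazard ratio of 2.5. Section 8.0 (Specific Aim 2, sample size) says "At 2 years, we hypothesize that a higher proportion of intervention participants will regress from microalbuminuria to normoalbuminuria", names the log-rank test, and claims "approximately 80% power if the rate of regression in the SOC arm is at least 12" per cent.

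**Analysis.** Section 8.0 (Specific Aim 2, analysis plan) states "We will test the hypotheses that regression and progression rates are different across arms using multivariable Cox regression models". It does not say what counts as an event or how it is dated. The sentence on the mixed model for 3-monthly uACR then carries a parenthesis: "primary endpoints obtained by evaluating the uACR and other key renal outcomes at 18 and 30 months". The reason given is that the maximum tolerated dose is not settled until 6 months after enrolment.

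**Follow-up.** Section 1.2: "Planned follow-up is two years for all participants". Section 5.0 schedules uACR "at baseline and then every 3 months while on study, until completing 2 years of followup". Section 9.0 repeats two years.

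**Entry.** Section 1.2 describes a two-sample mean in the microalbuminuric range. It also allows call-back of Aim 1 participants who were normoalbuminuric (particularly at 20-29 mg/g) or macroalbuminuric. The Section 3.0 inclusion list for Aim 2 asks for completion of Aim 1 and one repeat value of 30-300 mg/g.

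**The concern.** A stated primary timepoint cannot be observed on the stated schedule. The phrase sits in the mixed-model sentence but speaks of primary endpoints in the plural and of other renal outcomes, so it may or may not reach the two Cox endpoints. Those endpoints also lack an event rule. With eight follow-up samples per person, single crossing, two consecutive values and month-24 status can give different event counts from the same data.

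What is at stake is mainly prespecification. Section 6.0 C plans an interim look at efficacy whose results go to the DSMB and also to all relevant parties. Section 6.0 G has the DSMB reviewing primary endpoint analyses at least every six months. A rule still open at that point could be settled with results in view.

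**Working it through.** **1. Timing.** Scheduled post-baseline uACR values: 24 / 3 = 8, at months 3 to 24. Month 18 is on this schedule. Month 30 is 30 - 24 = 6 months after the last value. The plan's reason suggests where the numbers come from: 6 + 12 = 18 and 6 + 24 = 30, that is, 12 and 24 months after titration. This is an inference, and it would still need 30 months from enrolment.

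**2. Do two-year proportions clash with a Cox or log-rank analysis?** Inputs from Section 8.0: 126 per arm after 10% loss, alpha 0.017, and the stated rates and hazard ratios. Events d = 126 x (SOC rate + intervention rate). Power = Φ(√d x |ln HR| / 2 - 2.387), where 2.387 is the two-sided 0.017 normal quantile.

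| Endpoint | d | HR | Computed | Stated (140 per arm) |
|---|---|---|---|---|
| Regression, 12% vs 30% | 52.9, about 53 | 2.5 | 0.829 | 0.828 |
| Regression, 16% vs 40% | 70.6, about 71 | 2.5 | 0.930 | 0.928 |
| Progression, 60% vs 25% | 107.1, about 107 | 0.42 | 0.982 | 0.984 |

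The figures reproduce. The plan uses two-year cumulative proportions as event counts for a log-rank test, so the two framings are compatible. The tabulated HR is a ratio of proportions (0.30 / 0.12 = 2.50). Under proportional hazards, 12% and 30% imply ln 0.70 / ln 0.88 = 2.79. A true HR of 2.5 with 12% in SOC gives 1 - 0.88^2.5 = 27.4%, about 50 events and power 0.803, so the claim of about 80% stands.

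**3. Type I error.** Choosing the best of three rules, each at 1.7%, cannot exceed 3 x 1.7% = 5.1%. In a simulation (8 visits, 126 per arm, 12% true regression in both arms, within-person log SD assumed at 0.2, 0.3 or 0.5), each fixed rule gave 1.5-1.9%. The best of first crossing, month 18 and month 24 gave 3.5-4.9%. With noise only, the range was 1.8-4.8%, the low end being a sparse-event case.

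**4. Chance crossings.** The documents give no within-person SD, so 0.2 to 0.5 is assumed. With entry as Section 1.2 describes it (two-sample mean plus repeat value in range) and no true change, the proportion counted as regressed is:

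| Enrolled population | Any single value | Two consecutive | Month 24 only |
|---|---|---|---|
| Mid-range (Appendix B, Table S1) | 3.6-14.7% | 0.8-1.3% | 0.8-2.3% |
| Half at 30-59 mg/g (Section 5.0 strata, 140 of 280) | 16-58% | 4.7-21% | 4.2-17% |

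The effect on regression power depends on how treatment is assumed to act:
- *Assumed switch.* 12% vs 30% drop to 15 mg/g. At SD 0.2/0.3/0.5 with the strata mix, first crossing gives 44/32/16%, two consecutive values 64/55/38%, month 24 77/69/51%. With the Table S1 distribution: 78/69/39%, 79/77/64% and 87/84/72%.
- *The plan's hypothesised shift* (-40% vs +10%). Power is at least 96% (first crossing), 98% (two consecutive) and 87% (month 24).

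**5. Called-back participants.** If a person's true level is below 30 mg/g and log-scale error is symmetric and independent, each visit reads below 30 with probability above 0.5. At least one of eight does so with probability above 1 - 0.5^8 = 99.6%. Such a person counts as regressed under first crossing without any change. The mirror case is a true level above 300 mg/g. It is narrowed, not removed, by the Section 3.0 exclusion for an initial value above 300 combined with dipstick protein of 2+ or more. The number of such participants is unknown.

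**The case against.** The strongest reply is that the Cox and log-rank framing, with a two-year horizon, already implies first crossing by month 24, and that the 18/30-month phrase belongs to the mixed model alone. The compatibility part stands: a reader might infer that the two-year proportion contradicts the Cox analysis, and the power tables show that it need not. What remains is that the rule is unwritten and that the parenthesis is worded more broadly than the sentence it sits in.

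Second, the Background cites a cohort in which one normal uACR was enough to exclude microalbuminuria while a raised value needed confirming. This was a screening setting and does not define the trial endpoint, but it makes a single-value rule for regression supportable. A reader might infer that two-visit confirmation is required. The documents do not support that. In the switch scenario month-24 status had more power than confirmation in all six cells, and without noise confirmation lowers power from about 88-89% to 80-82%.

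Third, blinding balances measurement noise, so it does not inflate type I error. That stands for any rule fixed in advance. The DSMB is also independent and does not choose the endpoint, so error is inflated only if the study team chooses after seeing results.

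**Conclusion.** The timing conflict is certain and needs no assumption: a primary reading is placed 6 months after the last scheduled sample. The missing event rule is also plain on the text, for both regression and progression. Its consequence is conditional: error of about 3.5-5% instead of 1.7% if one of three rules is picked after the data are seen, under the assumed SDs.

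A reader might go further and infer that the trial is underpowered because of chance crossings. The documents do not support this. The loss rests on an undocumented within-person SD and an assumed switch model, and it is small under the shift that the plan hypothesises. Nor is the power arithmetic at fault, since it reproduces. What cannot be told is which event definition the 12%/16% and 60%/25% rates describe.

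**What to change.** In a dated SAP, before the first unblinded efficacy look:

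1. Replace the 18- and 30-month times in Section 8.0 with visits inside the 24-month schedule, month 24 being the last. If longer follow-up was intended, reconcile Sections 1.2, 5.0, 8.0 and 9.0. State whether the times apply only to the mixed model or also to the Cox endpoints.
2. Fix one event rule each for regression and progression (single crossing, two consecutive values, or month-24 status), and report one alternative as a sensitivity analysis. No particular rule is required.
3. State which definition the 12%/16% and 60%/25% rates describe, and check them against the within-person SD from the paired Aim 1 samples.
4. Add a sensitivity analysis excluding participants whose Aim 1 mean was outside 30-300 mg/g: below 30 for regression, above 300 for progression.

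The cost is SAP wording and minor extra analysis, since the 3-monthly uACR and the paired Aim 1 samples are already planned. The stated power may become slightly less favourable. Only a decision to extend follow-up would add visits.
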